- B) Premenopausal patients who have de-novo metastatic disease (metastatic disease at presentation).
- C) Premenopausal women who have not received Tamoxifen in the metastatic setting, but have received up to two lines of chemotherapy.

Post-Menopausal Women or Men

- D) Postmenopausal patients who have progressed on first-line or second-line therapy with an aromatase inhibitor in the metastatic setting
- E) Postmenopausal patients who have recurred while on or after completion of adjuvant treatment with aromatase inhibitors (they have completed at least one year of adjuvant AI in the adjuvant setting before progression on AI).
- F) Postmenopausal patients who are not considered candidates for treatment with an aromatase inhibitor by their oncologist , patients not willing not to go on to AI, or were intolerant to AI
- G) Post-menopausal women or men who have been treated with up to three lines in the escalation arm and up to two lines of chemotherapy in the dose expansion arm in the metastatic setting.

Type of Study

Open labeled, non-randomized; phase I dose escalation followed by phase Ib dose expansion

Prior Therapy

- Progression on any aromatase inhibitor for metastatic disease
- Recurrence ≥ 12 months after commencement of adjuvant aromatase inhibitors
- Patients are allowed (but not required) to have up to two prior chemotherapy regimens for metastatic disease

Rationale for Study

Cell cycle progression is directly regulated by cyclin-dependent serine-threonine protein kinases. The cyclin D proteins are important in cancer, as their abundance and functions are regulated by extracellular growth factor and adhesion signaling. The cyclin D proteins act through the CDK4 and CDK6 protein kinases to promote G1 progression (1). CDK4 and CDK6, in turn, hyperphosphorylate and activate the retinoblastoma protein Rb to promote cell cycle entry and cell proliferation. Consistent with their having an important role in human cancer, focal copy number abnormalities that result in increased CDK activity are among the most commonly described genetic events observed in diverse tumor types; these events

include amplifications of the genes that encode cyclin D1 or CDK4, and deletions affecting the CDKN2A locus, which encodes the p16INK4a inhibitor of CDK activity (2-4).

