Patient Population:

Patients with estrogen and/or progesterone receptor positive, HER2-negative advanced (metastatic) breast cancer that are in one of the following populations

Pre-menopausal Women:

- A. Pre-menopausal women who received adjuvant Aromatase Inhibitor and Ovarian Suppression (AI + OS) in the adjuvant setting and completed at least 12 months of hormonal therapy.
- B. Pre-menopausal women who have never been treated with endocrine therapy with de-novo metastatic disease.
- C. Pre-menopausal women who have not received Tamoxifen in the metastatic setting, but have received up to two lines of chemotherapy for dose expansion and up to three lines for dose escalation.

Post-Menopausal Women or Men

- D. Post-menopausal women or men who have progressed on first-line or second-line therapy with an aromatase inhibitor
- E. Post-menopausal women or men who have recurred while on or after completion of adjuvant treatment with aromatase inhibitors (they have completed at least one year of adjuvant AI in the adjuvant setting before progression on AI).
- F. Post-menopausal women or men who are not considered candidates for treatment with an aromatase inhibitor by their oncologist, refused AI, or intolerant to AI
- G. Post-menopausal women or men who have been treated with up to two lines of chemotherapy for dose expansion and up to three lines for dose escalation in the metastatic setting.

Total number of patients: 40

Number of Centers: 1 (will be adjusted, increased if accrual goals are not met).

Sample Size Justification (will be updated by statistician):

For a total of **40 subjects**, about 9-12 will be accrued during phase 1 portion and **about 30 patients for the phase 1b expansion.**

Part 1: phase 1 portion:

We will evaluate the first 9-12 patients in the phase I portion for safety.
The Primary objective is safety.

Part II: phase Ib expansion:

For the phase one expansion we will include pre- menopausal women, post-menopausal women, and men evaluated as one group. We will further evaluate both a three weeks on and one week off cohort (i.e. once daily for 21 consecutive days followed by a 7-day planned break) and a *continuous dose cohort* of ribociclib administered daily (QD) without a break in each cycle. Tamoxifen will be administered daily per standard of care in both cohorts.

The **primary objective** in the phase I study is to confirm safety, tolerability, confirm DLT, and determine the RP2D of Ribociclib with Tamoxifen

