The **secondary objective** is to evaluate 2 dose expansion cohorts after the maximum-tolerated dose (MTD) has been reached to better characterize the toxicity profile and identify early signs of efficacy. Our goal is to assess the anti-tumor activity Ribociclib + Tamoxifen and to further evaluate their safety in adult patients with HR+/HER2- locally advanced or metastatic breast cancer.

To determine whether treatment with ribociclib improves response rate (RR) compared to the historical response rate with treatment with Tamoxifen alone. We know that the expected RR for Tamoxifen after failure of first line AI is about 10 % and therefore we hypothesize an improvement of RR to 25%.

Efficacy Evaluation

Response and progression will be evaluated in this study using the new international criteria proposed by the Response Evaluation Criteria in Solid Tumors (RECIST 1.1). This will be expanded in protocol.

DEFINITIONS:

DLT – Dose-Limiting Toxicity

MTD – Maximum tolerated dose

PFS – Progression-Free Survival

DDI – Drug-Drug Interaction

ER – Estrogen Receptor

PR – Progesterone Receptor

HER2 – Human Epithelial Receptor 2

PO – by mouth (per orum)

SERMS (selective estrogen receptor modulators)

SOC – standard of care

RR- Response Rate

FIH – First in human

Protocol:

The TEEL Study: A Phase I trial of Tamoxifen with Ribociclib (LEE011) in adult patients with advanced ER+ (HER2 negative) breast cancer.

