1 BACKGROUND AND RATIONALE

1.1 Introduction

Breast cancer is one of the most common cancers in the Western Hemisphere and the second most common cause of cancer deaths in women. Endocrine therapy, including ovarian ablation; estrogen; and, more recently, antiestrogen administration, has been a major component of antitumor therapy in breast cancer for more than a century. Hormone sensitive metastatic breast cancer remains a therapeutic challenge despite the many recent advances in therapy. Barring a few exceptions, cure is not achieved in this disease. While hormonal interventions have clearly shown to decrease the tumor burden and to prolong life, the majority of patients eventually recurs and succumbs to their disease.

More than two thirds of all the advanced breast cancers are dependent on estrogen. Estrogen-withdrawal by physical removal of the ovaries or inhibition of their function has been one of the earliest successful interventions against breast cancer; however this intervention was limited to premenopausal women. The introduction of the SERMS (selective estrogen receptor modulators) has dramatically improved the survival of women with breast cancer, both pre and postmenopausal. The most prominent SERM is Tamoxifen, which until recently has been the gold standard for first-line therapy for women with advanced hormone-sensitive breast cancer. The introductions of several aromatase inhibitors (AIs) have added greatly to the arsenal against breast cancer and have replaced Tamoxifen as first-line therapy. The production of estrogen in postmenopausal women requires an enzyme called aromatase. This aromatase enzyme has been successfully blocked chemically. The most commonly used aromatase inhibitors include letrozole, anastrozole and exemestane.

However, the AIs are reserved for women who have naturally entered menopause or have their ovarian function suppressed. For premenopausal women or women who are unable to tolerate AIs, Tamoxifen remains the gold standard. In addition to that, there are many postmenopausal women who cannot tolerate the side effect profile of Aromatase Inhibitors. The response rate to first line hormonal therapy determined from four pivotal randomized Phase III trials ranges from 20-33% (1, 5, 6, 10). The response

rate to second line hormonal therapy is considerably less (10-20%) (6), suggesting a clear need for more effective therapy.

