10.2 Statistical Considerations for Phase Ib Dose expansion Study

If no MTD is observed with Level 1 through 3, we plan to continue/conduct the phase Ib dose expansion study as below. This expansion study is planned to understand and obtain initial efficacy data for the secondary endpoints.

Since the identical patient inclusion/exclusion criteria will be used in phase Ib dose expansion, all patient data from phase I dose escalation and phase Ib dose expansion studies can be combined for our statistical analysis, therefore, the required sample size of patients below will be both for phase I dose escalation and phase Ib dose expansion studies.

We obtained our statistical power and required sample size as a single-arm prospective study. In particular, for our evaluation of early efficacy we designed the study particular, for our evaluation of early efficacy we designed the study for testing $H_0: P \leq 0.10$ versus $H_1: P \geq 0.25$ at one-sided significance level 0.05 and power 0.80 as below.

P0	P1	Alpha	Beta	Cut-Off		Actual	Actual
				R + 1	N		
0.100	0.250	0.050	0.200	8	40	0.042	0.182

Where P0 is the maximum response proportion of standard care (tamoxifen alone), P1 is the minimum response proportion of our experimental treatment group, and N is the sample size.

For our statistical testing, if the number of responses $\geq R+1$, P0 is rejected based on Fisher's Exact test (34, 35). Alpha is the probability of rejecting that $P \leq P_0$ when this is true.

Beta is the probability of rejecting that $P \geq P_1$ when this is true.

Thus, the study requires 6 subjects under phase I dose escalation and 30 subjects under phase Ib dose expansion who will be treated with ribociclib (total 36) in order to test whether the proportion responding, P, is less than or equal to 0.100 or greater than or equal to 0.25. If the number of responses is 8 or more, the hypothesis that $P \leq 0.100$ is rejected with a target Type I error rate, α , of 0.050 and an actual error rate of 0.045. The null hypothesis will be rejected if 8 or more responses are observed in 40 patients. This design yields a type I error rate of 0.045 and power of 0.818 when the true response rate is 0.25.

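### The 10% null rate is stated only for tamoxifen after first-line AI failure but is applied to all pooled patients, so rejecting it would not by itself show improvement over tamoxifen alone

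*Combined protocol and SAP*

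**What the plan says.** The synopsis (Statistical Considerations, secondary objective) sets out to learn whether ribociclib raises the response rate above that seen historically with tamoxifen alone. It supports the benchmark with one sentence: "We know that the expected RR for Tamoxifen after failure of first line AI is about 10" percent. The hypothesised rate is 25%.

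Section 10.2 turns this into a one-sided exact test of P ≤ 0.10 against P ≥ 0.25, with rejection at 8 or more responses in 40. The condition on AI failure is gone: "P0 is the maximum response proportion of standard care (tamoxifen alone"). The analysis set is everyone, since "all patient data from phase I dose escalation and phase Ib dose expansion studies can be combined for our statistical analysis".

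The population is wider than first-line AI failure:

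- The synopsis Prior Therapy list fits the 10% setting fairly well ("Progression on any aromatase inhibitor for metastatic disease", or recurrence at least 12 months after starting an adjuvant AI).
- Group B must be endocrine-naive: "Pre-menopausal women who have never been treated with endocrine therapy with de-novo metastatic disease".
- Group C (Section 4, B.3) has no AI requirement.
- Group F (Section 4, C.3) takes patients who are not AI candidates, decline an AI or did not tolerate one.
- Group D covers more than first-line failure: "Post-menopausal women or men who have progressed on first-line or second-line therapy with an aromatase inhibitor".
- Group E is recurrence during or after an adjuvant AI.

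Section 1.1 gives rates that differ by line of hormonal therapy: "The response rate to first line hormonal therapy determined from four pivotal randomized Phase III trials ranges from 20-33" percent, and 10-20% for second line.

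**The concern.** A single-arm test against a historical rate is only as good as the match between the historical patients and those enrolled. Here the benchmark comes from one treatment history and is applied to a mixture. If the mixture would respond to tamoxifen alone more often than 10%, 8 responses in 40 could arise without any contribution from ribociclib more often than the plan's error rate suggests. A reader of a positive result would then credit ribociclib with something that may reflect who was enrolled. The documents contain no argument that 10% suits the pooled group, no weighting of the null by subgroup, and no restriction of the test to AI-failure patients.

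**Working it through.** **Inputs from the documents.** P0 = 0.10, P1 = 0.25, N = 40, reject at 8 or more (Section 10.2). First-line hormonal range 20-33%, second-line range 10-20% (Section 1.1).

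**Inputs assumed.** The number of first-line patients (4 or 10 of 40), the number of bone-only patients who cannot register a response (0 or 6), and a lower rate of 7% in heavily pretreated patients. The documents give none of these.

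**Step 1. The plan's own figure.** For X ~ Bin(40, p), the chance of rejection is P(X ≥ 8).

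- At p = 0.10: 0.0419, the table's 0.042.
- At p = 0.25: 0.818, so beta is 0.182, as in the table.

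The design table reproduces. The size of 0.042 belongs to the hypothesis P ≤ 0.10 and does not depend on who is enrolled.

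**Step 2. What the size means for the clinical question.** Let p be the rate the enrolled patients would show on tamoxifen alone. The chance of a false claim of improvement over tamoxifen is P(X ≥ 8 | 40, p). It is at most 0.042 if p ≤ 0.10. Otherwise:

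| Pooled tamoxifen-alone rate | P(8 or more of 40) |
|---|---|
| 0.10 | 0.042 |
| 0.11 | 0.067 |
| 0.12 | 0.100 |
| 0.15 | 0.244 |

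Solving P(X ≥ 8 | 40, p) = 0.05 gives p = 0.1036. The margin above 10% is under half a percentage point.

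**Step 3. Illustrative mixtures.** With k first-line patients at rate q, m patients who cannot respond, and the rest at rate r, the total is Bin(k, q) + Bin(40 − m − k, r), and P(total ≥ 8) comes from convolving the two. The two ends of each range are q = 0.20 and q = 0.33.

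| Non-responders m | Rate r in the rest | k = 4 | k = 10 |
|---|---|---|---|
| 0 | 0.10 | 0.066-0.106 | 0.117-0.283 |
| 6 | 0.10 | 0.030-0.054 | 0.063-0.191 |
| 0 | 0.07 | 0.015-0.029 | 0.044-0.151 |
| 6 | 0.07 | 0.006-0.014 | 0.024-0.101 |

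The error relative to tamoxifen alone can lie on either side of 0.042, depending on a mix that the plan does not fix.

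**Step 4. What a comparison restricted to first-line AI failure could do.** The lower limit of an exact 90% interval compared with 10% is a one-sided 0.05 test. Smallest rejecting counts, with size at 0.10 and power at 0.25:

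- 5/20: size 0.043, power 0.59.
- 6/27: size 0.047, power 0.70.
- 7/30: size 0.026, power 0.65.

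The full-sample power is 0.82. As examples of intervals, 4/20 gives 7% to 40%, which does not exclude 10%, and 7/30 gives 12% to 39%, which does.

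**The case against.** The strongest reply is that the test is correct as written. It addresses P ≤ 0.10, and its size for that hypothesis is 0.042 regardless of the mix. This stands, and it limits the point to what a rejection may be taken to mean.

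Second, the inflated figures rest on assumed numbers of first-line patients and on a 20-33% range that is not specific to tamoxifen and whose sources cannot be checked here. Some features lower the expected rate: escalation admits bone-only disease (usually non-measurable, although Section 11.6 accepts lesions measurable by MRI) and up to three chemotherapy lines. This also stands. With both effects included, most of the scenario range is at or below 0.05.

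Third, Section 3 lists no response comparison with historical tamoxifen. It speaks only of attempting to assess activity. The synopsis marks its sample-size text as still to be updated, and Section 10.2 seeks initial efficacy data. This lowers the importance. It does not remove the point, because the synopsis states the comparison as an aim and Section 10.2 sizes the study on it.

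The Prior Therapy list does not close the gap: it cannot bind group B, which must have had no endocrine therapy.

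A reader might go further and infer that the type I error is inflated, or that 10% is too low for this trial. The documents support neither. They do not give the mix or a tamoxifen-specific rate for patients without AI failure, and the factors they do describe pull in both directions.

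**Conclusion.** The point holds in a limited form. The 10% benchmark is supported only for tamoxifen after first-line AI failure, and the plan applies it to a population that by design includes other histories. Rejecting P ≤ 0.10 at 8/40 is a valid statement about a fixed 10% at size 0.042. It becomes a statement about improvement over tamoxifen alone at that error rate only if the enrolled patients would respond at 10% or less on tamoxifen, and the documents do not show this. The tolerance is narrow (about 10.4%), so a modest share of better-prognosis patients would matter. The mixture figures are illustrations, not estimates. Importance is minor to moderate: the aim is secondary and no go/no-go decision is tied to the test. Confidence is medium, since the mismatch is plain in the text but its direction and size are not known. Section 10.2 also states its sample size and actual alpha in two ways each. Those are separate matters, and this point does not depend on them.

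**What to change.** In Section 10.2 and the synopsis:

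1. State that the 10% rate refers to tamoxifen after failure of a first-line AI.
2. Keep N = 40 and the 8/40 rule as the sizing basis and as a test against a fixed 10% benchmark. Add that a rejection is evidence of early activity and does not prove improvement over tamoxifen alone in the mixed population.
3. Report response with exact 90% confidence intervals in three groups by AI history: first-line AI failure; other AI failure (second-line failure, or recurrence on or after an adjuvant AI); and no AI failure. Patients who were intolerant of an AI but did not fail it belong in the third group.
4. Compare with 10% only in the first-line AI-failure group. State that checking the lower 90% limit against 10% is a one-sided 0.05 test, and that its power at a true 25% would be about 0.59 with 20 patients and 0.65 to 0.70 with 27 to 30. The size of this group is not known in advance.

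The cost is a few sentences and one table. AI history is already needed for eligibility, and neither sample size nor enrollment changes. The downside is a weaker efficacy claim and wide intervals. In a group of ten, for example, 2/10 gives 4% to 51%.

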1 BACKGROUND AND RATIONALE

1.1 Introduction

Breast cancer is one of the most common cancers in the Western Hemisphere and the second most common cause of cancer deaths in women. Endocrine therapy, including ovarian ablation; estrogen; and, more recently, antiestrogen administration, has been a major component of antitumor therapy in breast cancer for more than a century. Hormone sensitive metastatic breast cancer remains a therapeutic challenge despite the many recent advances in therapy. Barring a few exceptions, cure is not achieved in this disease. While hormonal interventions have clearly shown to decrease the tumor burden and to prolong life, the majority of patients eventually recurs and succumbs to their disease.

More than two thirds of all the advanced breast cancers are dependent on estrogen. Estrogen-withdrawal by physical removal of the ovaries or inhibition of their function has been one of the earliest successful interventions against breast cancer; however this intervention was limited to premenopausal women. The introduction of the SERMS (selective estrogen receptor modulators) has dramatically improved the survival of women with breast cancer, both pre and postmenopausal. The most prominent SERM is Tamoxifen, which until recently has been the gold standard for first-line therapy for women with advanced hormone-sensitive breast cancer. The introductions of several aromatase inhibitors (AIs) have added greatly to the arsenal against breast cancer and have replaced Tamoxifen as first-line therapy. The production of estrogen in postmenopausal women requires an enzyme called aromatase. This aromatase enzyme has been successfully blocked chemically. The most commonly used aromatase inhibitors include letrozole, anastrozole and exemestane.

However, the AIs are reserved for women who have naturally entered menopause or have their ovarian function suppressed. For premenopausal women or women who are unable to tolerate AIs, Tamoxifen remains the gold standard. In addition to that, there are many postmenopausal women who cannot tolerate the side effect profile of Aromatase Inhibitors. The response rate to first line hormonal therapy determined from four pivotal randomized Phase III trials ranges from 20-33% (1, 5, 6, 10). The response

rate to second line hormonal therapy is considerably less (10-20%) (6), suggesting a clear need for more effective therapy.

1.2 Tamoxifen

Tamoxifen is the most commonly used anti-estrogen or SERM; it is currently being used in the prevention of breast cancer, for ductal carcinoma in situ, in women with early stage breast cancer and for those with metastatic cancer. It is generally well tolerated and due to its extensive use, its toxicities and long-term sequelae are well characterized. Women being treated with Tamoxifen may experience flushing (similar to those women experience during the menopause), vaginal dryness and vaginal discharge. The most serious side effects are the slightly increased risk of thromboembolic events. In a trial involving 900 women treated with either Tamoxifen or letrozole, 9 out of 455 patients treated with Tamoxifen experienced a thromboembolic event (2%), compared to 3 patients out of 455 in the group treated with letrozole (<1%). Other side effects included hot flashes (25%), headaches (5%), fatigue (5%) and nausea (8%) (5). The observation of endometrial cancer (<0.5%) has been predominantly observed when used in the preventive or adjuvant setting (4). Hence, the cumulative administration of Tamoxifen is rarely hampered by toxicity but rather by the emergence of resistance suggested by clinical progression while on the drug.

1.3 CDK Inhibitors

A promising new class of drugs showing activity in cancer is CDK Inhibitors. Cell cycle progression is directly regulated by cyclin-dependent serine-threonine protein kinases. The cyclin D proteins are important in cancer, as their abundance and functions are regulated by extracellular growth factor and adhesion signaling. The cyclin D proteins act through the CDK4 and CDK6 protein kinases to promote G1 progression (1). CDK4 and CDK6, in turn, hyperphosphorylate and activate the retinoblastoma protein Rb to promote cell cycle entry and cell proliferation. Consistent with their having an important role in human cancer, focal copy number abnormalities that result in increased CDK activity are among the most commonly described genetic events observed in diverse tumor types; these events include amplifications of the genes that encode cyclin D1 or CDK4, and deletions affecting the CDKN2A locus, which encodes the p16INK4a inhibitor of CDK activity (2-4).

Data from The Cancer Genome Atlas highlight the importance of the Cyclin/CDK/Rb pathway in breast cancer (2, 3). Abnormalities that result in CDK activation are highly enriched in the luminal A and B molecularly defined subgroups, ~85% of which were ER+/Her2- (5). Cyclin D1 amplifications were observed in 29% and 58% of the luminal A and B subtypes, respectively, and CDK4 amplifications were observed in 14% and 25% of luminal A and B subtypes, respectively. Luminal A subtype tumors also have loss of CDKN2C, which encodes p16Ink4a, a CDK inhibitor. The luminal subtypes also maintain expression of Rb, which would be essential for benefit from treatment with a CDK4/6 inhibitor (2-4).

PD0332991 is an oral, potent, selective inhibitor of CDK4/6 that was shown to inhibit proliferation and induce apoptosis in multiple preclinical models of endocrine-resistant breast cancer, both in vitro and in vivo (4, 11). In the clinic, PD0332991 was studied in a randomized Phase II study in combination with the non-steroidal aromatase inhibitor letrozole. This combination significantly prolonged median progression free survival in postmenopausal women with locally recurrent or advanced ER+/HER2+ breast cancer treated in the front-line setting (median PFS 26.1 vs 7.5 months, reported in Finn et al (6).

Most breast tumors that initially respond to anti-estrogen therapy acquire resistance in time. Given the above pre-clinical data, there may be benefit from a combination of Tamoxifen and Ribociclib, in women with hormone sensitive tumors as well as those whose tumors became unresponsive. Current and recently completed studies restrict CDK trials and limit the patient population to only postmenopausal patients but it is well known that younger, pre-menopausal and peri-menopausal patients often have more “aggressive” disease and more endocrine-resistant disease and this combination may be very helpful in delaying endocrine resistance in this patient population.

